10.6 Continuation of treatment with Investigational Product

This is an exploratory study in volunteers who will have no medical benefit from the treatment and thus there will be no treatment after end of study participation.

10.7 Treatment compliance

All IP will be administered at the research clinic under supervision of trained study personnel to ensure compliance.

10.8 Return and destruction of investigational products

Any unused study product and all empty containers will be destructed at the site upon confirmation from the Sponsor. The Monitor will perform final IP accountability reconciliation at the study end to verify that all unused IP is adequately destroyed and documented.

11 STUDY ASSESSMENTS

The study assessments are described in the sections below and the timing of these assessments are detailed in the schedule of events (PART A: Table 8.1-1 and PART B: Table 8.1-2)

11.1 Recording of data

The Principal Investigator will provide the Sponsor with all data produced during the study from the scheduled study assessments. He/she ensures the accuracy, completeness, legibility, and timeliness of the data reported to Sponsor in the eCRF and in all required reports.

11.2 Demographics and other baseline characteristics

11.2.1 *Informed consent*

Signed informed consent must be obtained before any screening procedures are initiated. The informed consent procedure is further described in Section 14.3.

11.2.2 *Eligibility criteria*

Eligibility criteria should be checked during screening and verified before IP administration. The criteria are specified in Sections 9.4 and 9.5.

11.2.3 *Demographic information*

The following demographic data will be recorded: gender, age, ethnicity and race.

11.2.4 ***Weight and height***

Weight and height will be measured without shoes. BMI will be calculated with one decimal from the height and weight recorded.

11.2.5 ***Medical/surgical history***

Medical/surgical history will be obtained by subject interview in order to verify that the eligibility criteria are met.

The medical/surgical history should include all relevant diseases and surgeries within 2 months prior to screening as judged by the Investigator.

11.2.6 ***Prior and concomitant medication***

Prior medications taken within 2 weeks will be obtained by subject interview in order to verify that the eligibility criteria are met (see also Section 9.6.2).

Medications are classified as prior if the stop date was before or on the day of the first dose administration (pre-dose) and as concomitant if ongoing on the day of the first dose administration, stopped after the first dose administration or started after the first dose administration. To distinguish between prior and concomitant medications on Day 1 in each part (i.e. the first IP administration), the start time of any newly introduced medication or the stop time of any previously ongoing medication must be recorded in the eCRF.

Any use of concomitant medication from screening until the last end-of-study visit must be documented appropriately in the subject's eCRF. Relevant information (i.e. name of medication, dose, unit, frequency, start and stop dates, reason for use) must be recorded. All changes in medication should be noted in the eCRF.

11.2.7 ***HIV and Hepatitis B/C***

Subjects will be tested for HIV, hepatitis B surface antigen and hepatitis C antibodies prior to inclusion into the study. Any positive result will exclude the subject from participating in the study.

11.2.8 ***Urine drug screen***

Urine will be screened for drugs of abuse at timepoints outlined in the schedule of events (Table 8.1-1 and Table 8.1-2) using the Alere™ Drug Screen Test Panel.

11.2.9 ***Alcohol breath test***

An alcohol breath test will be performed at timepoints outlined in the schedule of events (Table 8.1-1 and Table 8.1-2).

11.2.10 ***Baseline symptoms***

A baseline symptom is defined as an event that occurs between the subject's signing of the ICF until the insertion of the arterial catheter (i.e. an event that occurs during the screening

period). Such events are not AEs and will be recorded as baseline symptoms in the Medical History Log in the eCRF.

11.2.11 *Clinical laboratory profile*

Blood samples for analysis of clinical chemistry and haematology will be collected through venepuncture or an indwelling venous catheter and sent to the certified clinical chemistry laboratory at Uppsala University Hospital and analysed by routine analytical methods.

The clinical laboratory parameters are defined in Table 11.2-1 and will be assessed at screening.

Abnormal values assessed by the Investigator as clinically significant will be reported as baseline symptoms. If an abnormal value is associated with corresponding clinical signs or symptoms, the sign/symptom should be reported in the Medical History Log in the eCRF.

Table 11.2-1 Clinical laboratory parameters

Category	Parameter
Clinical chemistry	Alanine aminotransferase (ALT)
	Aspartate aminotransferase (AST)
	Creatinine
	Glucose
Haematology	Haematocrit
	Haemoglobin (Hb)
	Platelet count
	Red blood cell (RBC) count
	White blood cell (WBC) count
FSH-test (at screening, postmenopausal females only in questionable cases)	FSH
	Estradiol

11.2.12 *Physical examination*

A complete physical examination will include assessments of the head, eyes, ears, nose, throat, skin, thyroid, neurological, lungs, cardiovascular, abdomen (liver and spleen), lymph nodes and extremities.

Physical examination will be judged as normal, abnormal, not clinically significant or abnormal, clinically significant. The assessment will be recorded in the eCRF.

11.2.13 *Resting 12-lead ECG*

Single 12-lead ECG will be recorded in supine position after 10 minutes of rest using an ECG machine. HR and PR, QRS, QT and QTcF intervals will be recorded.

ECGs will be reviewed and interpreted on-site by the Investigator.

Any abnormalities will be specified and documented as clinically significant or not clinically significant.

11.3 Assessments related to PET-endpoints

11.3.1 *Inhalation training*

At the end of the screening visit subjects, who consented to study participation and are found eligible (awaiting results of clinical laboratory sampling), will perform inhalation training with the *myblu*™ e-cigarette. Training will be held by study personnel at the research site.

Inhalation training will be performed on dummy (nicotine free) devices and once on a regular *myblu*™ e-cigarette (containing nicotine corresponding to the formulations used during PET). Training on a nicotine-containing device is considered necessary for the subjects for them to be used to the experience when inhaling in the PET-camera.

Inhalation training on dummy devices (nicotine free) may be repeated in the morning of Visit 2 (before PET), if considered necessary by the study personnel or the subject.

11.3.2 *Insertion/removal of arterial catheter*

After a positive modified Allen test, an intraarterial catheter will be inserted preferably in the arteria radialis of the non-dominant arm if possible, else in another artery chosen by the anaesthesiologist. Local anaesthetics e.g. 0.5 mL of Xylocain® (active substance lidocaine) 10 mg/mL may be applied for the arterial cannulation at the discretion of the anaesthesiologist inserting the cannula.

Positive modified Allen test: If the hand flushes within 5-15 seconds, this indicates that the ulnar artery has good blood flow; this normal flushing of the hand is considered to be a positive test.

Negative modified Allen test: If the hand does not flush within 5-15 seconds, this indicates that ulnar circulation is inadequate or non-existent; in this situation, the radial artery supplying arterial blood to that hand should not be punctured.

The arterial catheter will be removed by trained personnel at the research clinic after the (last) PET session is completed. When the catheter is withdrawn, pressure should be applied to the injection site for approximately 10 minutes until bleeding ceases. The catheter is checked to see that it is intact.

11.3.3 *Assessment of blood radioactivity*

Discrete blood samples will be analysed using an in house developed well counter detector system cross-calibrated with the PET/CT scanner.

Serial discrete arterial blood samples with a volume of approximately 5 mL (2 mL used for each analysis) will be collected in test tubes for the analysis of radioactivity in whole blood withdrawn at specified timepoints (Section 11.3.4 and 11.3.5). The time of sampling will be recorded in the middle of the sampling period by using a foot pedal linked to a computer and the test tubes will be labelled with barcodes for identification. Data will be stored directly in separate files, one for each PET/CT-scan session, including sample weight, number of counts and time of measurement. The data will be corrected for physical decay of ¹¹C to the time for tracer inhalation. The samples will be destructed directly after measurement.

11.3.4 PET/CT (PART A)

Administration/inhalation and subject preparation

The subject will be moved from the research site to the PET-Centre approximately 30 minutes before the PET-scan.

The subject is positioned in the PET-CT camera and a ULDCT scan is performed to correct for attenuation of the photons and to outline the anatomy. In supine position the subject inhale from the device, without changing the head or body position. The PET-CT operator takes the inhalation device and the PET-scan begins.

The inhalation device is measured before and after inhalation to determine total amount of [¹¹C]nicotine delivered to the subject. The amount of [¹¹C]nicotine lost when the subject exhales cannot be determined.

PET-protocol

PET-scan 1: The subject inhales (1-2 puffs) for about 3-5 seconds to receive about 10-24 µL solution corresponding to approximately 25 MBq [¹¹C]nicotine. A dynamic 40 min PET scan is performed with the oral cavity/throat and large bronchi in field-of-view (20 cm). Arterial blood is collected as discrete samples of 5 mL each, taken at 2, 4, 6, 8, 10, 15, 20 and 30 minutes to determine radioactivity in whole blood.

PET-scan 2: The subject inhales (1-2 puffs) for about 3-5 seconds to receive about 10-24 µL solution corresponding to approximately 25 MBq [¹¹C]nicotine. A dynamic 40 min PET scan is performed with part of the lung in field-of-view (20 cm). Arterial blood is collected as discrete samples of 5 mL each, taken at 2, 4, 6, 8, 10, 15, 20 and 30 minutes to determine radioactivity in whole blood.

For both lung and oral cavity scans, the dynamic PET data is acquired in list mode, and will initially be reconstructed into 6 x 10s, 3 x 20s, 2 x 30s, 2 x 60s, 2 x 150s and 6 x 300s frames. The scanner will be started 30 seconds before the tracer administration. The data collected 30 seconds before inhalation will not be reconstructed. The registration of data is depending on the resulting images, the frame definition may be optimised, taking the inhalation protocol into account. The static scans over lung and oral cavity will be acquired as single frame scans of 600s.

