7 STUDY OBJECTIVES AND ENDPOINTS

7.1 Primary objectives (PART A only)

The primary objectives are:

- To measure the amount of nicotine deposited in the lungs and the oral cavity during 40 minutes after administration of ^{11}C -labelled nicotine via the *myblu™* e-cigarette system using PET

7.1.1 *Primary endpoint (PART A only)*

The primary endpoints are:

- Dynamic PET Digital Imaging and Communications in Medicine (DICOM) images over the lungs and oral cavity 0-40 minutes after administration
- Radioactivity vs. time profiles for the lungs and oral cavity 0-40 minutes after administration

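### Section 11.3.4 states the PET scan start in two incompatible ways; the narrative order would lose the opening 10 s frames of the primary curves

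*Protocol*

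**What the plan says.** Two parts of Section 11.3.4 fix when the Part A scan starts.

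- **Administration and preparation paragraph.** After the attenuation CT, "In supine position the subject inhale from the device, without changing the head or body position". The next sentence is "The PET-CT operator takes the inhalation device and the PET-scan begins". Read in order: inhale, hand over the device, start the scan.
- **Acquisition paragraph.** "The scanner will be started 30 seconds before the tracer administration", and "The data collected 30 seconds before inhalation will not be reconstructed". Read in order: start the scanner, wait 30 s, inhale, and build frames from inhalation onwards.

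Section 11.3.5 repeats the second rule, including the discarded lead-in, for the Part B brain scan. The first sentence appears only in the Part A section.

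The time axis is anchored elsewhere. The primary endpoint in Section 7.1.1 is "Radioactivity vs. time profiles for the lungs and oral cavity 0-40 minutes after administration". Section 11.3.3 corrects the blood counts for decay back to the moment of tracer inhalation. The Part A frames are "6 x 10s, 3 x 20s, 2 x 30s, 2 x 60s, 2 x 150s and 6 x 300s frames". The acquisition is in list mode, and the section allows the frame scheme to be adjusted later in light of how the inhalation was done.

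**The concern.** The two sentences describe different acquisitions. Under one, the camera is recording when the subject draws on the device. Under the other, it starts only after the puff or puffs, the inhalation into the lungs and the hand-over.

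The beginning of the primary curves depends on which is followed. The scheme puts six 10 s frames in the first minute, so the protocol wants fine resolution there. Section 6.2 gives the purpose as finding out whether the two formulations reach different parts of the respiratory tract, and the first seconds after inhalation bear on that. The scheduled discrete blood samples start at 2 minutes, so they cannot stand in for missing early images.

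Consistency matters because the groups are small (5 subjects per formulation) and because the oral cavity and the lung are imaged in separate sessions after separate administrations. A start that varied between sessions would leave some curves without early points that others have.

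**Working it through.** **1. Reproduce the stated scan length.** Inputs: the frame lists in Sections 11.3.4 and 11.3.5. Formula: sum of (number of frames × frame length).

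- Part A: 6×10 + 3×20 + 2×30 + 2×60 + 2×150 + 6×300 = 60 + 60 + 60 + 120 + 300 + 1800 = 2400 s = 40.0 min, in 21 frames. The section states 40 min.
- Part B: the same with 4×300 at the end = 60 + 60 + 60 + 120 + 300 + 1200 = 1800 s = 30.0 min, in 19 frames. The section states 0-30 min.

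Both stated lengths are reproduced.

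**2. Ask which start rule fits.** The frame total alone does not decide this, since 2400 s of frames could follow any start. The endpoint does: it runs from 0 to 40 min after administration.

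| Scan start | Pre-inhalation data | Acquisition needed to cover 0-40 / 0-30 min | Are the first frames acquired? |
|---|---|---|---|
| 30 s before administration | 30 s, discarded | 2400 + 30 = 2430 s = 40.5 min / 1800 + 30 = 1830 s = 30.5 min | Yes, all six |
| After inhalation and hand-over, delay d | None | Cannot cover the interval from 0 to d | No, not before d |

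Only the lead-in rule delivers the endpoint as defined.

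**3. Size the loss under the narrative order.** The protocol gives no time from inhalation to hand-over, so d is an assumption. Number of 10 s frames lost = d/10, up to 6.

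| Assumed d | 10 s frames lost, of six |
|---|---|
| 5 s | 0.5 (first frame truncated) |
| 10 s | 1 |
| 20 s | 2 |
| 30 s | 3 |
| 60 s | 6 |

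One component has a figure in the document. Section 10.5 describes 1-2 puffs of 3-5 s each, so puffing alone takes 1×3 = 3 s to 2×5 = 10 s, before any gap between puffs, the inhalation into the lungs or the hand-over. If zero is the start of the first puff, that by itself covers between 30% and all of the first frame.

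**4. Put the loss in proportion.** A delay of 10-30 s is 10/2400 = 0.4% to 30/2400 = 1.25% of the scan time. If frames were instead counted from a late scanner start, the curve would be shifted by d. For d = 30 s and an assumed carbon-11 half-life of 20.4 min, physical decay over the shift is 1 − 2^(−0.5/20.4) = 1.7%. For oral activity, Section 6.3 cites an earlier PET study with 45% of the administered amount at the end of inhalation and 8% at 45 min. That implies a half-life of 45 × ln 2 / ln(45/8) = 18.1 min and a change of 1 − 2^(−0.5/18.1) = 1.9%. The later curve is therefore barely touched; what is at risk is the first minute.

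**The case against.** The strongest reply is that the intended rule is plain. The lead-in is explicit and numeric, sits in the acquisition paragraph, has its own data-handling instruction and is repeated for Part B. The other sentence is a loose description of the procedure. This is a single-centre study, and a PET Centre would probably run the scan correctly. The scan that begins after hand-over could also be read as the analysed scan. Finally, list-mode data can be re-framed around the actual inhalation.

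Much of this stands. It shows which sentence should give way, and it makes a widespread error unlikely. It does not remove the contradiction. The analysed data begin at inhalation, not after hand-over, so the lenient reading does not fit either. Re-framing helps only for data that were recorded.

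Three stronger readings are tempting, and the documents do not support them.

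- *A reader might infer that time zero and the first frames are undefined.* They are defined. Sections 7.1.1, 11.3.3 and 11.3.4 all refer to administration or inhalation, and the frame list starts where the discarded lead-in ends. Which instant of one or two puffs counts as zero is a residual imprecision of about one 10 s frame, which an operating manual can settle. Section 11.3.3 does provide for exact blood timing: "The time of sampling will be recorded in the middle of the sampling period by using a foot pedal linked to a computer".
- *A reader might infer that the last 300 s frame is 30 s short*, because a 40 min scan started 30 s early leaves 39.5 min. Nothing says that acquisition stops 40 min after scanner start. The frame totals and the endpoint point to 40 min analysed plus the lead-in.
- *A reader might infer that an early peak of known importance is lost.* No figure in the protocol shows such a peak or its size.

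**Conclusion.** The point holds as an internal contradiction in Section 11.3.4: the scan cannot start both after hand-over and 30 s before administration. Time zero is inhalation, and the frame scheme together with the endpoint agrees with the lead-in rule, so the narrative sentence is the one out of line. If it were followed, the inhalation would not be imaged and the opening frames of the primary 0-40 min curves would be lost or truncated: 1 to 3 of six 10 s frames for an assumed hand-over of 10-30 s. The direction of that loss follows from the text, but its size rests on the assumed delay.

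The effect is confined to the first part of the curve, and no document figure says how much information lies there. Correction is worthwhile because the loss would fall on the primary endpoint, could not be repaired at analysis, and is avoided by changing one sentence. The conflict is direct only for Part A. Part B would be affected only if the site applied the Part A administration sequence there.

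**What to change.** In Section 11.3.4, rewrite the sentence on the operator taking the device so that the scanner is already running from 30 s before inhalation and continues without interruption while the device is handed over. State that frames, blood sample times and decay correction all refer to the same recorded inhalation time.

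For clarity, add in Sections 11.3.4 and 11.3.5 that the 30 s lead-in is additional to the 40 min (Part A) and 30 min (Part B) of analysed data, which makes acquisitions of 40.5 and 30.5 min.

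The exact puff instant used as zero, and any logging of a second puff or of hand-over, can be left to the imaging manual.

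The cost is a few words in the protocol. There is no extra scanner time if the lead-in is already planned as additional, and at most 30 s per scan if it is not.

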17.4 Description of study population

17.4.1 *Demographics and baseline characteristics*

Descriptive statistics for demographics, weight and height will be presented by treatment and study part.

17.4.2 *Medical/surgical history and prior/concomitant medication*

Medical/surgical history will be presented by system-organ-class (SOC) and preferred term (PT). Prior/concomitant medications will be presented by ATC level 1, 3 and 5.

All data will be listed by subject.

17.4.3 ***Treatment compliance***

The number of subjects treated with each formulation in each part will be listed.

17.4.4 ***Physical examination***

Clinically significant and non-clinically significant abnormal findings will be specified and presented by subject and summarised by treatment and study part.

All data will be listed by subject.

17.4.5 ***12-lead ECG***

All ECGs will be categorised as "normal", "abnormal, not clinically significant", or "abnormal, clinically significant" (as judged by the Investigator) and summarised by treatment and study part using frequency tables.

All data will be listed by subject.

17.4.6 ***Clinical laboratory analyses***

Clinical laboratory data will be summarised by treatment and study part.

Abnormal, clinically significant values will be summarised separately if considered appropriate.

All data will be listed by subject.

17.5 **Analysis of PET endpoints**

The PET Centre will be responsible for evaluation of PET data, and present time activity data on deposition during the dynamic scans in PET-scan 1 and 2. For the evaluation of [¹¹C]nicotine kinetics in the lung, primary bronchi, oral cavity and airways, volumes of interest (VOIs) will be delineated, and time activity data generated utilising PET-image analysis software. The VOIs will be delineated based on the anatomical information from the low dose CT-images combined with the uptake seen in the PET images. Deposition in the lungs will be measured and presented for one large VOI covering the entire lung.

Furthermore, a small VOI may be delineated to be representative for deep lung tissue, however this VOI will not include the entire deep lung tissue. Even though alveolar tissue cannot be identified in detail on the ULDCT or PET images, the highest density of alveolar tissue, combined with lowest density of bronchi and major blood vessels, will be found in the peripheral part of the lung and a small VOI will be delineated at a position representative for deep lung tissue.

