For PET-scan 3 acquired over the brain, the amount of nicotine distributed to the brain will be estimated. A whole brain VOI will be delineated on the T1-MR images overlaid on the brain PET-image. This part of the study is explorative and dependent on the time course of the [¹¹C]nicotine uptake to the blood and the time activity uptake for brain nicotine may be difficult to measure with a sufficient signal-to-noise ratio.

The uptake data will be stored in spreadsheet format and sent to study sponsor to enable further data analysis. Furthermore, and as an exploratory part of the PET-image analysis, other regions may be delineated and analysed, if visual inspection of overlaid PET and ULDCT images shows substantial uptake in other tissues or regions.

Input data for evaluation of [¹¹C] uptake and distribution:

- Amount of radioactivity administered from inhalator (inhalator measured before and after inhalation)
- PET-images showing deposition of radioactivity in the lung
- PET-images showing deposition of radioactivity in the oral cavity
- Radioactivity measured in arterial blood.

The relative amount of radioactivity that is deposited in the lung can be determined from the activity measured in the PET images and the known amount of activity in the inhalator before and after the inhalation.

Blood radioactivity data will be collected processed and stored in excel spreadsheets.

Time course of delivered nicotine as well as fraction that reach lung or is deposited in oral cavity, throat and large bronchi will be tabulated and sent to the study sponsor as excel files. The radioactivity measured continuously in arterial blood as well in the discrete blood samples will tabulated in excel sheets and sent to the study sponsor.

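### Lung deposition is to be presented for the entire lung, but the lung scan images only part of it, so a lung amount or fraction read as whole-lung leaves out the unimaged lung

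*Protocol*

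**What the plan says.** The primary objective in section 7.1 is "To measure the amount of nicotine deposited in the lungs and the oral cavity during 40 minutes after administration". Part A has two scans on one day, each after its own inhalation and at least 2 hours apart (section 8.1.1). PET-scan 1 views the mouth, throat and large bronchi. PET-scan 2 is the lung scan, and section 11.3.4 describes it so: "A dynamic 40 min PET scan is performed with part of the lung in field-of-view (20 cm").

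Section 17.5 then states: "Deposition in the lungs will be measured and presented for one large VOI covering the entire lung". An optional small VOI may stand for deep lung, with a caveat: "however this VOI will not include the entire deep lung tissue". The large VOI carries no such caveat.

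Section 17.5 also says how the lung share is obtained: "The relative amount of radioactivity that is deposited in the lung can be determined from the activity measured in the PET images", together with the device activity measured before and after inhalation. The "fraction that reach lung or is deposited in oral cavity, throat and large bronchi will be tabulated" and sent to the sponsor.

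Section 11.3.4 mentions static scans once: "The static scans over lung and oral cavity will be acquired as single frame scans of 600s". Their bed position, timing and use are not given.

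**The concern.** The acquisition section and the analysis section disagree about how much lung is measured. The numerator of the lung fraction can hold only activity inside the 20 cm field of PET-scan 2. The denominator is everything the device delivered. Nothing in the protocol limits the label to imaged lung, scales up for the rest, or combines bed positions.

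The study rationale (section 6.2) is to learn where in the respiratory tract nicotine from each formulation lands. If the lung share is understated and the oral share is not, the balance between them is misread. The shortfall would also go unnoticed: section 11.3.4 says exhaled activity cannot be determined, so the mass balance cannot be closed, and activity in unimaged lung looks the same as activity breathed out.

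**Working it through.** **Passages side by side**

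| Item | Section | Content |
|---|---|---|
| Lung in PET-scan 2 | 11.3.4 | part of the lung, 20 cm |
| VOI for lung deposition | 17.5 | the whole lung |
| Numerator of lung fraction | 17.5 | activity in the PET images |
| Denominator | 17.5 | activity delivered, from device readings before and after inhalation |
| Correction for unimaged lung | – | none stated |

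Let c be the share of lung activity inside the field of view. Then reported lung fraction = c × true lung fraction, and understatement = 1 − c. The first two rows of the table together imply c < 1 unless the unimaged lung holds no activity.

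**Can the static scans fill the gap in the 0-40 min profile?** The dynamic frames are "6 x 10s, 3 x 20s, 2 x 30s, 2 x 60s, 2 x 150s and 6 x 300s frames":

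60 + 60 + 60 + 120 + 300 + 1800 = 2400 s = 40 min.

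The dynamic acquisition fills the whole period at one bed position. A separate 600 s frame cannot supply the missing lung for that curve.

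**Size (illustration only).** The protocol has no stated figure to reproduce and gives neither lung length L nor the spread of deposition along it. Both are assumed here, with all 20 cm of the field lying on lung.

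Uniform deposition, c = 20/L:

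| L (cm) | c | Understatement |
|---|---|---|
| 20 | 100% | 0% |
| 22 | 90.9% | 9.1% |
| 25 | 80.0% | 20.0% |
| 28 | 71.4% | 28.6% |
| 30 | 66.7% | 33.3% |

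Non-uniform deposition, c = 20/(20 + r(L − 20)), where r is deposition per cm in unimaged lung relative to imaged lung:

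| L (cm) | r | c | Understatement |
|---|---|---|---|
| 25 | 0.5 | 20/22.5 = 88.9% | 11.1% |
| 25 | 2 | 20/30 = 66.7% | 33.3% |
| 30 | 0.5 | 20/25 = 80.0% | 20.0% |
| 30 | 2 | 20/40 = 50.0% | 50.0% |

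**Between formulations.** If c is the same in every subject, it cancels in a ratio of the two formulations. If mean c happened to be 0.70 in one group of 5 and 0.90 in the other (assumed values), the apparent ratio would be 0.70/0.90 = 0.78 with no true difference. Nothing in the protocol suggests which way such an imbalance would go.

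**The case against.** **Entire lung may mean all lung in view.** The sentence is followed at once by the small deep-lung VOI, so the contrast may be large against small, and section 11.3.4 states the partial coverage openly. This is a plausible reading. But the text does not say so, and on this reading the tabulated lung fraction is still mislabelled and is understated if taken as whole-lung.

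**The static scans may cover the rest.** They are described as over the lung, without the limit placed on PET-scan 2, and one static frame could in principle supply an amount at a single time. The frame-sum argument answers this for the curve only. For the amount, the answer is that section 17.5 bases deposition on the dynamic scans, the synopsis speaks of two body positions, and nothing links the static scans to the lung result. Their coverage remains unknown and should be stated.

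**PET-scan 1 may show some upper lung,** since the large bronchi are in view. It follows a separate inhalation, so its activity cannot simply be added to that of scan 2, and the protocol plans no combination.

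**The impact is limited.** The listed primary endpoints are images and radioactivity-time profiles, no formulation test is specified, and profiles per mL are not biased low in this way. That stands, and it confines the point to the amount and the fraction. The amount is nevertheless what the primary objective names.

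**The size is assumed throughout.** Also true. The 0% end means full coverage, which does not fit the statement that only part of the lung is in view, and the 50% end pairs the longest assumed lung with an unsupported r of 2. The contradiction does not depend on these figures.

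**Conclusion.** The concern holds. Sections 11.3.4 and 17.5 cannot both be right as written, and the disagreement bears on the quantity named in the primary objective. The lung amount and fraction describe imaged lung. Presented as whole-lung values they are too low, by an amount the documents do not allow one to calculate: 0-33% under uniform deposition and lung lengths of 20-30 cm, and 11-50% in the non-uniform cases shown, all resting on assumed lengths and profiles. Coverage will differ with lung size and positioning, which adds noise between two small non-randomised groups; no bias towards either formulation is shown. This should be fixed before the data are analysed, but it does not make the study unworkable.

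**What to change.** - **Section 17.5:** define the large VOI as *all lung tissue within the field of view*, and label the lung amount and fraction *imaged-lung deposition*. Say that the lung part of the primary objective is addressed on that basis.
- **Section 11.3.4:** place the 20 cm field on the same anatomical landmark in every subject. State what the 600 s static scans cover, when they are taken and what they are used for. If they are meant to supply the rest of the lung, say how they enter the lung amount and word the VOI definition to match.
- **Reporting:** give each subject's imaged lung volume, from the ULDCT already acquired, next to the lung fraction. Keep the amount and fraction as the lung result; a per-litre value is at most a supportive summary.
- **Whole-lung figure:** give one only as a labelled extrapolation, and only if the existing CT covers the whole lung or the assumption used is stated.

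The cost is wording in two sections, a positioning instruction and one volume readout per subject. No added scan, radiation or visit is needed. The protocol does not say that the ULDCT reaches beyond 20 cm, so a CT-based extrapolation may not be possible, and no wider CT is proposed. The price is that the headline result becomes imaged lung rather than whole lung.
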